14.7 Clinical Study Report

The results of the study will be presented in an integrated CSR in accordance with ICH guidelines.

15 ETHICAL CONSIDERATIONS

15.1 Good Clinical Practice Statement

The clinical study will be performed in accordance with the protocol, the Declaration of Helsinki, ICH Guidelines, GCP and all applicable local regulatory requirements.

15.2 Institutional Review Board

The final study protocol and informed consent form (ICF) must be approved, in writing, by the relevant IRB before patient enrollment commences.

The following information should be reported to the IRB (*in accordance with local requirements*) during the study:

- All amendments to the clinical research study.
- Annual progress reports.
- Individual SUSARs.
- Urgent safety measures.

15.3 Patient Information and Consent

Prior to performing any study-related activities, including screening tests and procedures, written informed consent must be obtained from the patient, in accordance with local regulations.

The ICF must be in accordance with the principles that originated in the Declaration of Helsinki, current ICH and GCP guidelines, applicable regulatory requirements and Sponsor policy and must be approved by the prevailing IRB for each study center.

15.4 Subject Data Protection

Personally identifiable information, i.e., identifiable information from or about an individual subject, will not be collected by the Sponsor. The collection and processing of data from patients enrolled in this study will be limited to those data that are necessary to investigate the clinical activity, safety, tolerability, quality and utility of the study drug used in this study. These data must be collected and processed with adequate precautions to ensure confidentiality and compliance with applicable data privacy protection laws and regulations.

The ICF must explain that identifying information will be kept by the Investigator on file and that portions of the patient's medical records pertinent to the study will be reviewed by Sponsor personnel (or their designees) and possibly by Regulatory Agencies and the IRB for data verification purposes.

16 ADMINISTRATIVE PROCEDURES

16.1 Quality Assurance

In compliance with GCP and regulatory requirements, the Sponsor/designee, external Regulatory Agency and/or /IRB may conduct quality assurance (QA) audits at any time during or following completion of the study. The Investigator will be expected to cooperate with any audit and to provide assistance and documentation (including source data) as requested.

16.2 Case Report Form and Source Document Verification

Electronic CRFs will be provided for recording clinical data. Designated site personnel will record data in the eCRF for observations, tests and assessments as specified in the protocol. The Sponsor will provide eCRF completion guidelines to assist site personnel.

Data required for the eCRF should be completed in a timely manner so as to aide Sponsor and CRO management.

The Investigator must permit the Sponsor/designee reasonable direct access to designated source documentation (e.g., medical records) for the purpose of verifying that the data recorded in the eCRF are consistent with the original source data.

16.3 Study Monitoring

Before a patient can be screened for enrollment into the study, the Sponsor/designee will conduct a study initiation visit to:

- Determine that site facilities are adequate.
- Discuss responsibilities with regard to the protocol with the Investigator and the study team.
- Conduct training on completion of the eCRF and other study- related documentation.
- Review study procedures.

During the conduct of the study, the Sponsor/designee will provide ongoing support to the Investigator and study team. The Sponsor/designee will conduct regular site visits, according to applicable ICH and GCP guidelines, to:

- Confirm the facilities remain acceptable.
- Confirm the site study team is adhering to the protocol and regulatory requirements.
- Confirm that the investigational product is being properly maintained and accountability records are accurate and current.
- Confirm data are being accurately recorded in the eCRF by performing source document verification.
- To intervene and stop any serious protocol non-compliance by a site and if required report to IRB and the Regulatory Authority.

16.4 Retention of Study Data

A copy of all records and essential documents must be retained in the study files for a minimum of 2 years following the last approval of the drug in an ICH region and until there are no pending or contemplated marketing applications in an ICH region, or a minimum of 2 years have elapsed since the formal discontinuation of the clinical development of the drug. No documents should be destroyed without prior written agreement between the Sponsor and the Investigator and/or clinical site.

Should the Investigator wish to assign the documents to another party or move them to another location, prior approval of the Sponsor must be obtained. The Sponsor will notify the Investigator in writing when any study-related documents are no longer needed.

16.5 Use of Information and Publication Policy

All information regarding BGB324 and the Sponsor's operations (e.g., patent applications, formulas, manufacturing processes, basic scientific data, or formulation information) supplied by the Sponsor to the Investigator and not previously published is considered confidential. This confidential information remains the sole property of the Sponsor and shall not be disclosed to others without the written consent of the Sponsor. The Investigator agrees to use this information only to perform this study and will not use it for other purposes, including publication or presentation without the Sponsor's written consent. The full terms of confidentiality, intellectual property and publication policy are detailed in the current Clinical Trial Agreement between the Sponsor and the site.

16.5.1 Clinical research organizations

Monitoring, data management, statistics and programming, pharmacovigilance, medical writing, auditing and QA services will be outsourced to the Sponsor's CRO.

Pharmacokinetic and pharmacodynamic analyses will be outsourced to the Sponsor's bioanalytical services vendors.

16.5.2 Changes to the final study protocol

All protocol amendments must be submitted to the IRB and Regulatory Authorities.

Protocol amendments that affect patient safety, the scope of the investigation, or the scientific quality of the study should not be implemented without prior IRB approval, except where necessary to eliminate immediate hazards to the patients.

16.5.3 Investigator responsibilities

By signing the protocol the Investigator agrees to:

- Conduct the study in accordance with the protocol and make changes only after so directed by the Sponsor, except to protect the safety, rights or welfare of patients.
- Personally conduct or supervise the study.
- Inform any patients enrolled in the study that BGB324 is being used for investigational purposes.
- Ensure that the requirements relating to obtaining informed consent and IRB review and approval meet federal guidelines, as stated in 21CFR50 and 21CFR56.
- Report to the Sponsor any AEs that occur during the course of the study, in accordance with 21CFR312.32, as well as ICH guidelines.
- Have read and understood the Investigator's Brochure for BGB324, including potential risks and side effects of the drug.
- Maintain adequate and accurate records, in accordance with 21CFR312.62 and to make those records available for inspection by the Sponsor, its designated representatives, relevant Regulatory Authorities, the IRB or any agency authorized by law.
- Ensure that an IRB that complies with the requirements of 21CFR56 will be responsible for initial and continuing review of the clinical study.
- Report promptly to the IRB and the Sponsor all changes in the research activity and all unanticipated problems involving risks to patients or others (to include protocol amendments and IND safety reports).
- Not make any changes in the research study without approval, except when necessary to eliminate hazards to the subject/subjects.
- Comply with all other requirements regarding the obligations of Clinical Investigators and all other pertinent requirements listed in 21CFR312.
- Ensure that all associates, colleagues and employees assisting in the conduct of the study are informed about their obligations in meeting the above commitments.
- Enter data collected from patients into the eCRF as soon as possible i.e. within 5 working days of the respective visit.

18 APPENDICES

Appendix 1 ECOG Performance Status Scale

Grade	ECOG Performance Status
0	Fully active, able to carry on all pre-disease performance without restriction
1	Restricted in physically strenuous activity but ambulatory and able to carry out work of a light or sedentary nature, e.g. light house work, office work
2	Ambulatory and capable of all selfcare but unable to carry out any work activities. Up and about more than 50% of waking hours
3	Capable of only limited selfcare, confined to bed or chair more than 50% of waking hours
4	Completely disabled. Cannot carry on any selfcare. Totally confined to bed or chair
5	Dead

Appendix 2 The NYHA Functional Classification in a Subject with Heart Disease

Overview: The NYHA developed a functional classification for subjects with heart disease.

Subjects: Heart disease must be present.

Parameters:

- Limitations on physical activity

Symptoms (undue fatigue palpitations dyspnea and/or anginal pain) with ordinary physical activity

- Status at rest

Functional Capacity	Objective Assessment
Class I. Patients with cardiac disease but without resulting limitation of physical activity. Ordinary physical activity does not cause undue fatigue, palpitation, dyspnea, or anginal pain.	A. No objective evidence of cardiovascular disease.
Class II. Patients with cardiac disease resulting in slight limitation of physical activity. They are comfortable at rest. Ordinary physical activity results in fatigue, palpitation, dyspnea, or anginal pain.	B. Objective evidence of minimal cardiovascular disease.
Class III. Patients with cardiac disease resulting in marked limitation of physical activity. They are comfortable at rest. Less than ordinary activity causes fatigue, palpitation, dyspnea, or anginal pain.	C. Objective evidence of moderately severe cardiovascular disease.
Class IV. Patients with cardiac disease resulting in inability to carry on any physical activity without discomfort. Symptoms of heart failure or the anginal syndrome may be present even at rest. If any physical activity is undertaken, discomfort is increased.	D. Objective evidence of severe cardiovascular disease.

http://my.americanheart.org/professional/StatementsGuidelines/ByPublicationDate/PreviousYears/Classification-of-Functional-Capacity-and-Objective-Assessment_UCM_423811_Article.jsp#.VsXt6ZOLR-U

Appendix 3 Drugs that are Generally Accepted to Have a Risk of Causing Torsades de Pointes

Generic Name	Brand Name
Amiodarone	Coradone/Pacerone
Anagrelide	Agrylin®, Xagrid®
Arsenic trioxide	Trisenox
Astemizole	Hismanal
Azithromycin	Zithromax®, Zmax®
Bepridil	Vascor
Chlorquine	Arelan
Chlorpromazine	Thorazine
Cisapride	Propulsid
Citalopram	Celexa®, Cipramil®
Clarithromycin	Biaxin
Cocaine	Cocaine
Disopyramide	Norpace
Dofetilide	Tikosyn
Domperidone	Motilium
Dronedarone	Multaq®
Droperidol	Inapsine
Erythromycin	Erythrocin/E.E.S.
Escitalopram	Cipralex®, Lexapro®
Flecainide	Tambocor®, Almarytm®
Halofantrine	Halfan
Haloperidol	Haldol
Ibutilide	Covert
Levomethadyl	Orlaam
Mesoridazine	Serentil
Methadone	Methadose/Dolophine
Moxifloxacin	Avelox
Ondansetron	Zofran®, Anset®
Petamidine	NebuPent/Pentam
Pimozone	Orap
Probucol	Lorelco
Procainamide	Pronestyl/Procan
Quinidine	Cardioquin/Quinaglute
Sevoflurane	Ulane®, Sojourn®
Sotalol	Betapace
Sparfloxacin	Zagam
Sulpiride	Dogmatil®, Dolmatil®
Terfenadine	Seldane
Thioridazine	Mellaril
Vandetanib	Zactima

Adapted from "The University of Arizona Center for Education and Research on Therapeutics." See the following website for an updated list of drugs that cause Torsades de Pointes: www.AZCERT.org

Appendix 4 NCI CTCAE, Version 4.03

NCI CTCAE Version 4.03 of the, dated 14 June 2010, may be found at the following website:
http://evs.nci.nih.gov/ftp1/CTCAE/CTCAE_4.03_2010-06-14_QuickReference_5x7.pdf

SMC	Safety Monitoring Committee
TEAE	Treatment-Emergent Adverse Event
TTP	Time To Progression
WHO	World Health Organization
WBC	White Blood Cells

1 Introduction

This document presents the statistical analysis plan (SAP) for BerGenBio ASA, Protocol No. BGBC004: A Multi-Center Open-Label Phase 1/2 Study of BGB324 in Combination with Erlotinib in Patients with Stage IIIb or Stage IV Non-Small Cell Lung Cancer (NSCLC). This Statistical analysis plan (SAP) is based on the final protocol dated 16 May 2017 (Version 5.0).

This study is designed primarily to evaluate the safety of the Axl inhibitor BGB324 when administered as monotherapy, and to establish the recommended Phase 2 dose (RP2D) of the combination of BGB324 and erlotinib in patients with Stage IIIb or Stage IV NSCLC.

2 Study Objectives

2.1 Run-In Cohort (Phase 1)

2.1.1 Primary Objective

To explore the safety and tolerability of single agent BGB324 in patients with NSCLC.

2.2 Arm A (Phase 1)

2.2.1 Primary Objective

- To identify the RP2D of BGB324 administered in combination with erlotinib in patients with NSCLC

2.2.2 Secondary Objectives

The **secondary objectives** are:

- To explore the safety and tolerability of BGB324 administered in combination with erlotinib in patients with NSCLC.
- To identify the dose limiting toxicity (DLT) profile of BGB324 administered in combination with erlotinib in this population.
- To assess the pharmacokinetics (PK) of BGB324 and erlotinib and the potential effect of BGB324 on erlotinib.

2.2.3 Exploratory Objective

- To evaluate the pharmacodynamics (PD) effects of BGB324 administered in combination with erlotinib.

2.3 Arm B (Phase 2)

2.3.1 Primary objective

- To explore the safety and tolerability of the combination of BGB324 and erlotinib in patients with NSCLC with an activating Epidermal Growth Factor Receptor (EGFR) mutation and who have progressed after receiving an approved EGFR inhibitor (i.e., prior erlotinib, afatinib or gefitinib).

2.3.2 Secondary Objectives

The **secondary objectives** are:

- To assess the PK of BGB324.

- To explore the clinical efficacy of the combination of BGB324 and erlotinib in this setting.

2.3.3 Exploratory objectives

The **exploratory objectives** are:

- To evaluate the PD effects of BGB324 administered in combination with erlotinib.
- To investigate any correlation between the PD effects of BGB324 administered in combination with erlotinib and clinical efficacy.

2.4 Arm C (Phase 2)

2.4.1 Primary Objective

- To explore the safety and tolerability of the combination of BGB324 and erlotinib in the first-line setting in patients with advanced NSCLC with an activating EGFR mutation.

2.4.2 Secondary Objectives

- To explore the time to progression of the combination of BGB324 and erlotinib in this setting.

2.4.3 Exploratory Objectives

The **exploratory objectives** are:

- To evaluate the PD effects of BGB324 administered in combination with erlotinib.
- To investigate any correlation between the PD effects of BGB324 administered in combination with erlotinib and clinical efficacy.

3 End-points

3.1 Safety End-points

Safety and tolerability will be assessed by conducting the following safety assessments at pre-defined time-points during the study:

- Treatment emergent adverse events (TEAE)
- Physical examination
- Vital signs including blood pressure (BP), heart rate (HR)
- Electrocardiogram (ECG) or multi-gated acquisition (MUGA) scan
- 12-lead triplicate ECG
- Clinical laboratory parameters including clinical chemistry, hematology coagulation and urinalysis
- Eastern Co-operative Oncology Group (ECOG) performance status

The primary objective of Arm A is to identify the RP2D of BGB324 administered in combination with erlotinib in patients with NSCLC. This will be accomplished by evaluation of the safety and occurrence of DLTs at each dose level.

AEs will be assessed using the National Cancer Institute (NCI) Common Toxicity Criteria for Adverse Events (CTCAE) Version 4.03 criteria during the first cycle (21 days) of treatment for the purposes of establishing the dose of BGB324 that can safely be given in combination with erlotinib.

DLTs will include:

- Any non-hematological toxicity \geq Grade 3 except Grade 3 nausea, vomiting or diarrhea that resolves within 72 hours with optimal therapy;
- Grade 4 thrombocytopenia or Grade 3 thrombocytopenia with bleeding.
- Grade 4 neutropenia persisting for \geq 5 days or Grade 3 or 4 febrile neutropenia.
- Treatment discontinuation or dose reduction for $>$ 72 hours during the first cycle as a result of treatment-related toxicity.

A patient must receive all loading doses and miss no more than 3 daily doses in Cycle 1 (21 day cycle of treatment) to be considered as informative to support dose escalation, unless the inability to administer BGB324 was a result of treatment-related toxicity.

If 1 patient in a cohort experiences a DLT during Cycle 1, the cohort will be expanded to 6 patients. If 2 of 3 or 2 of 6 patients in a cohort experience DLT, no further dose-escalation will take place and the prior dose level will be nominated as the RP2D (see section 8.3.2 of the protocol).

3.2 Efficacy End-points

Disease assessment will be performed after every two cycles (6 weeks) of treatment prior to administering study drug in the subsequent cycle. The frequency of scans may be extended to the end of every three cycles after 12 weeks (4 cycles) and every 4 cycles after 24 weeks (8 cycles). Patients who remain on treatment for 12 months or longer may have their scans extended to a frequency of 6 months, unless disease progression is suspected in which case a scan should be conducted at an earlier time point.

Clinical efficacy will be assessed using the Response Evaluation Criteria in Solid Tumors (RECIST) Version 1.1. Clinical efficacy endpoints will include time to progression.

3.2.1 Objective Response Rate (ORR)

Patients included in the study must be assessed for response to treatment, Overall Response (OR) determined by Investigator based on appropriate radiographic imaging and consistent with RECIST 1.1.

Each patient will be assigned to one of the following ordered categories for OR (from best to worst responses): Complete response (CR), Partial response (PR), Stable disease (SD), Progressive disease, Not Evaluable (NE) or Not Applicable at each timepoint.

The Best Overall Response (BOR) is determined once all the data for the patient is known and is defined as the best overall response recorded from the initiation of treatment until disease progression or date of subsequent therapy across all tumour assessment.

ORR defined as percentage of patients with a BOR assessed as CR or PR, i.e. patients with response, divided by the number of patients in efficacy population.

The one-sided, within-group tests of proportion of responders, against the null hypothesis of a response rate $\leq 5\%$ (this being the observed response rate under current treatment). Values of $p < 0.2$ will be taken as sufficient evidence of a trend to justify further study.

For analysis of the ORR, summary tables will be generated, presenting the number and percentage of responders (i.e. patients with CR or PR) and non-responders in efficacy population.

3.2.2 Best Percentage change in target lesion

Percentage change in target lesion size from baseline across all tumour assessment, where target lesion size is measured by the sum of the product of diameters of all target lesion sizes by the Investigator.

The Best percentage change is largest percentage change across all tumour assessment.

Patients who die due to progression of their disease prior to the first planned protocol assessment of response will be considered as having BOR of PD.

The first response assessed during the follow-up period will be used to confirm any previous CR or PR observed during the treatment period, provided that no new anti-tumoral treatment has been initiated during the follow-up period.

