10.1.5 End-of-study visit

The following assessments will then be carried out at the EOS visit (28 days after the last dose of study drug) for every patient enrolled into the study.

- Performance status assessment.
- Physical examination.

- Vital signs.
- Serial 12-lead ECGs, in triplicate
- MUGA/ECHO.
- Serum pregnancy test.
- Clinical chemistry, hematology, coagulation and urinalysis.
- Blood sampling for PK
 - PK sampling in Arm B will be for BGB324 only - see Table 6.
- Disease assessment (if not performed within previous 28 days).
- Drug accountability.
- AEs assessment.
- Concomitant medications assessment.

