3.2.3 Time To Progression (TTP)

- The Time to Progression (TTP) will be calculated as the number of days from the date of first administration of BGB324 to the date of radiological progression of disease first observed, according to the overall response evaluation (progressive disease, measurement proven or progressive disease, symptomatic deterioration). If a subject died without any radiological assessment, the progressive disease date is date of death;

Patients who do not have progressive disease at the end of study or withdrawal will have their TTP censored. In these patients, the censoring date is defined as the last date on which progression status was assessed. Censoring general rules for TTP are provided within [Table 1](#) below.

Table 1: Censoring Rules for TTP

Reason for censoring	Rule
No baseline evaluable or post-baseline radiological assessment	Date of first treatment administration
Two or more not evaluable (NE) protocol specified assessments, i.e. scheduled assessments, before progressive disease	Date of last evaluable disease protocol specified assessment before the second protocol specified NE assessment
No progressive disease	Date of last evaluable radiological assessment
Treatment discontinuation for undocumented progression	Date of last evaluable radiological assessment
Treatment discontinuation for toxicity or other reason	Date of last evaluable radiological assessment

* An assessment is considered NE when no imaging/measurement is done at all at a particular time point, or only a subset of lesion measurements are made at the time point. The participant is considered NE at that time point.

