5.7.3 Method of analysis for efficacy outcome

5.7.3.1 Objective Response Rate (ORR)

Response criteria for target lesions and non-target lesions (see [Section 3.2](#)) will be evaluated at each disease assessment and will be presented in a data listing by subject.

In addition, the presence/absence of new lesions will be collected at each disease assessment and will be presented in a data listing by subject.

The investigator will evaluate the target/non-target lesion response criteria and status (presence/absence) of new lesions against the RECIST Version 1.1 criteria to determine overall response for the appropriate disease assessment time point.

Although all efficacy analysis for this study is to be regarded as essentially exploratory, there will be a formal hypothesis test for the objective response rate here (Arm B only). Specifically, for a given disease assessment time point we denote subjects who achieve a CR or a PR Best overall response. The null hypothesis is that the proportion of objective responders (i.e., the ORR) is less than or equal to 5%. The alternative hypothesis is that the proportion of objective responders is greater than 5%. The binomial test will be used to conduct the hypothesis test at the one-sided significance level of 0.2.

Overall response and the ORR will be presented within a data listing by subject and time point.

Best overall Response (BOR) will also be listed.

The number and percentage of each BOR class will be described by cohort.

Moreover, the Sum of Target Lesion Measurements (STLM) will be analyzed from relative changes from baseline and graphically displayed with waterfall plot in order to visualize changes in sum of lesion without differentiating best response categories.

Best response to therapy will be defined as the Best Changes from Baseline in Sum of Target lesions measurement for a patient during the study.

The Best Percentage change in STLM will be calculated as, $STLM = 100 * (\text{Value of STLM} - \text{Baseline value STLM}) / \text{Baseline value STLM}$;

In case of several post baseline assessments of STLM the one with the lowest change (i.e., showing the best diminution of sum of lesions relative to baseline) will be considered.

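### Best percentage change and TTP lack the subsequent-therapy cut-off that the SAP sets for best overall response, so a late scan can count in one efficacy output and not in another (minor)

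*SAP*

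**What the plan says.** Three efficacy outputs are built from the same scans.

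- **BOR (SAP 3.2.1)** is the "best overall response recorded from the initiation of treatment until disease progression or date of subsequent therapy across all tumour assessment". ORR and the Arm B binomial test are derived from it.
- **Best percentage change (SAP 3.2.2 and 5.7.3.1)** starts from the "Percentage change in target lesion size from baseline across all tumour assessment", and then: "The Best percentage change is largest percentage change across all tumour assessment". SAP 5.7.3.1 describes it as the "Best Changes from Baseline in Sum of Target lesions measurement for a patient during the study" and settles the choice among scans: "In case of several post baseline assessments of STLM the one with the lowest change" is used. It feeds Table 14.2.2 and the waterfall plot (Figure 14.2.2).
- **TTP (SAP 3.2.3, Table 1; analysed for Arm C in 5.7.3.2)**. For patients without progression: "In these patients, the censoring date is defined as the last date on which progression status was assessed". Table 1 has rows for discontinuation but none for new anticancer therapy.

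SAP 3.2.2 also lets a follow-up scan confirm an earlier CR or PR, "provided that no new anti-tumoral treatment has been initiated during the follow-up period". That condition applies to confirmation only.

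At the end-of-study (EOS) visit, Protocol 10.1.5 lists "Disease assessment (if not performed within previous 28 days". The visit falls 28 days after the last dose, or at study withdrawal (Protocol 8.9, SAP 4.3.3). Protocol 11.4 and SAP 4.4.1 bar other NSCLC treatment during the study period, which under Protocol 8.6 and SAP 4.3 includes the EOS visit.

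**The concern.** The SAP gives no reason for using different windows. Its BOR definition recognises that scans may exist after progression or after the next treatment starts, and sets them aside. The same scans stay eligible for best percentage change. If new treatment starts before progression is documented, they also stay eligible for TTP.

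One such scan is enough to matter for a patient, because best change is a single extreme value and a censoring date is a single last date. A patient with a BOR of progressive disease could show a shrinking bar in the waterfall plot. In Arm C, TTP is the only secondary objective, and it could gain event-free time, or take a progression event, observed under another treatment. Arm B has at most 25 patients and Arm C at most 14, so even one or two such patients would be visible.

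**Working it through.** The SAP states no figure on this point, so there is none to reproduce. The check compares the rules and then bounds the exposure.

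**1. The rules applied to the same late scan**

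| Scan at EOS | BOR | Best % change | TTP |
|---|---|---|---|
| After documented progression | excluded | included | no effect; the event has already occurred |
| After new therapy, no earlier progression | excluded | included | included, as a censoring date or as an event |

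The first row needs no new treatment, only a scan after progression. It affects best change alone.

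**2. Length of the exposed period**

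Only one assessment is scheduled after treatment ends, at EOS, so at most one scheduled scan per patient is exposed. Using the SAP's 30.4375 days per month:

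- 28 / 30.4375 = 0.92 months from last dose to EOS.
- (28 + 7) / 30.4375 = 35 / 30.4375 = 1.15 months if the 7-day window in Protocol Table 5 is used in full as a delay.
- If EOS takes place at study withdrawal, the period can be shorter.
- If the bar on other NSCLC treatment is followed up to EOS, time on a new drug is 0 days and no scan is affected by new therapy.

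**3. How often an EOS scan is made**

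Suppose EOS is exactly 28 days after the last dose. A scan made d days before the last dose is then 28 + d days old, so a new scan is due for any d above 0. But the Table 5 window row is headed (+/-). In the same row, Day 21 of Cycle 2 shows +5, while footnote p lets that scan be made up to 5 days early. If EOS may likewise fall 7 days early, on day 21 after the last dose, a scan up to 7 days before the last dose still satisfies the exemption (21 + 7 = 28). A scan made after the last dose can satisfy it too. The documents therefore do not fix how many patients have an EOS scan.

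**4. Illustration, best change (assumed values)**

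Baseline sum 50 mm, 62 mm at progression, 34 mm at an EOS scan.

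- At progression: (62 − 50) / 50 = +24%.
- At EOS: (34 − 50) / 50 = −32%.

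The stated rule plots −32%, while BOR remains progressive disease. This is an extreme case: the fall from 62 to 34 mm is 28 / 62 = 45%.

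**5. Illustration, TTP (assumed values)**

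Scan without progression on day 42, stop for toxicity on day 60, new therapy on day 67, EOS scan without progression on day 88 (60 + 28). The day-42 scan is 46 days old at EOS, so a scan is due.

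- Read literally, Table 1 censors at day 88: 88 / 30.4375 = 2.89 months.
- With a cut-off at new therapy, it censors at day 42: 42 / 30.4375 = 1.38 months.
- Difference: 46 days, or 1.51 months. Of these, 88 − 67 = 21 days were spent on the new therapy. The other 25 days came before it, but were shown to be event-free only by a scan made under it.

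**The case against.** The strongest objection is that the situation is prohibited. No other NSCLC treatment may be taken before the EOS visit, no tumour follow-up is planned after it, and patients with major deviations may be excluded from the efficacy analysis. This limits the size of the problem but does not close the gap. Patients who stop BGB324 are withdrawn from the study, so it is unclear whether the bar still binds them until EOS. A conduct rule also does not tell the analyst what to do with a scan that exists. Nor does the bar prevent a scan after progression, which BOR excludes and best change includes.

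Second, the discontinuation rows of Table 1 may already be meant to end TTP follow-up at discontinuation, since otherwise they repeat the row for no progressive disease. On that reading the 46-day difference in the illustration vanishes. The reading is possible, but the rows say only that the last evaluable assessment is used, not that it must precede discontinuation or new therapy.

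Third, the confirmation condition in SAP 3.2.2 is weak evidence that new treatment was foreseen. Table 14.2.1 states that confirmation is not required, and leukaemia terms in the SAP's abbreviation list suggest template text. The cut-off in the BOR definition does not depend on that condition.

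Fourth, following patients regardless of new therapy is a legitimate choice for TTP. The SAP does not say that it makes that choice.

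A reader might infer that shrinkage or event-free time from the next treatment is routinely credited to BGB324, or that nearly every patient has a contaminated EOS scan. The documents support neither. They give no rate of early new therapy, they prohibit it, and step 3 of the working shows that the frequency of EOS scans depends on how the visit window is read.

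**Conclusion.** The inconsistency stands as a matter of text. BOR has a cut-off at progression or subsequent therapy, best percentage change has neither, and TTP Table 1 has no rule for new therapy. A late scan can therefore enter the waterfall plot, Table 14.2.2 and, where new therapy precedes progression, the Arm C TTP, while BOR leaves it out.

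The severity is minor. At most one scheduled scan per patient is exposed. The number of patients affected is unknown and may be zero. The affected outputs are descriptive, and the SAP calls all efficacy analysis essentially exploratory. A reader might extend the point to ORR or to the Arm B hypothesis test. That would be wrong, because both rest on BOR, which already has the cut-off. The two illustrations use assumed values to show how the rules work. They are not estimates of bias.

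**What to change.** In SAP 3.2.2 and 5.7.3.1, give best percentage change the BOR window, for example: *Best percentage change is the lowest percentage change from baseline among post-baseline assessments up to and including first documented progression and before the start of any subsequent anticancer therapy.*

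In SAP 3.2.3, add a row to Table 1. Reason: *Start of subsequent anticancer therapy before documented progression.* Rule: *Date of last evaluable radiological assessment before that start.* State that ongoing erlotinib is not subsequent therapy, and that this row takes precedence over the discontinuation rows and over a progression first seen later.

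The cost is about two sentences and one table row. The only extra data item is the start date of new therapy, which the BOR rule already needs. The downside is that a few patients may lose some weeks of TTP follow-up.
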